3.3.10 Calculation of modal dose

Modal dose categories will be calculated across all study days on or after the day of first dose of BRV in EP0132 and up to and including the day of last dose of BRV in the Evaluation Period (excluding the Down-Titration Period). Modal dose is calculated as the most frequently taken daily dose category during this period. Modal dose will be categorized as defined in [Table 3-6](#).

Table 3-6: Dose group definitions for calculation of modal dose

Daily dose category (mg/day) ^a	Equivalent mg/kg/day ^b	Dose group label
>0 to <100	>0.0 to <2.0	>0.0 to <2.0 mg/kg/day
≥100 to < 150	≥2.0 to <3.0	≥2.0 to <3.0 mg/kg/day
≥150 to <200	≥3.0 to <4.0	≥3.0 to <4.0 mg/kg/day
≥200	≥4.0	≥4.0 mg/kg/day

^a Daily dose category is modified for participants weighing less than 50kg.

^b For participants weighing ≥50kg, the dose in mg/kg/day is calculated based on a weight of 50kg. The permitted dose range for all participants is between 1 and 4 mg/kg/day.

To calculate modal dose, the following steps will be applied:

1. The total daily dose in mg/kg/day will be classified into 1 of the above categories on a daily basis
 - All participants are assigned 100 mg/day (or equivalently 2.0 mg/kg/day for study participants weighing less than 50kg) at the EV.
 - At the Telephone Call visit, the dose may be adjusted to 50 to 200mg/day (or equivalently 1.0 to 4.0 mg/kg/day for study participants weighing less than 50kg). This is documented on the Study Drug Dispensation and Administration eCRF. If 'maintain dose' is selected, the dose is continued from the EV. If 'modify dose' is selected then the new dose is documented in mg/day, and will be used to calculate the daily dose in mg/kg/day. It is assumed that any new dose is first taken the morning after it is dispensed.
 - Any subsequent changes to the daily dose in mg/day will be documented on the Study Drug Collection Dispensation and Administration eCRF. If 'maintain dose' is selected, the dose is continued from the 'daily dose at last visit' entered on the eCRF at that visit. If 'modify dose' is selected, then the new dose is documented in mg/day and will be used to calculate the daily dose in mg/kg/day.
 - For participants with body weight <50kg, the total daily dose in mg/kg/day will be the total daily dose in mg divided by the most recently available body weight in kg.
 - For participants with body weight ≥50kg, the total daily dose in mg/kg/day will be the total daily dose in mg divided by 50kg.
 - Each daily dose will then be classified into 1 of the daily dose categories in mg/kg/day. The total daily dose will be attributed to a specific period (the Evaluation Period and additionally a 3-month period as defined in [Table 3-3](#)).
2. Once all total daily doses are converted to mg/kg/day and classified into 1 of the above categories, the modal dose is the dose category which was most frequent within the specific period. In the event of a tie, the modal dose will be set to the lower of the tied dose categories.

The modal dose category will be calculated for each 3-month period the participant enters regardless of the number of days completed in this period. A participant is considered to enter a

period if the end date of the Evaluation Period is on or after the first day of the relevant 3-month period.

3.4 Possibly clinically significant values

PCST values are any laboratory measurements, vital signs or ECG parameters which meet the criteria defined in [Section 13.1](#) which occur any time after the first dose of BRV has been taken in EP0132. PCS criteria are based on Food and Drug Association Division of Neuropharmacological Drug Products guidelines with some UCB-defined additions. Assessment of whether a measurement fulfils age-dependent PCS criteria will be performed using the age of the participant in years at the visit. Measurements that meet PCS criteria and are treatment-emergent will be considered PCST regardless of whether or not they met the criteria for PCS previously.

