3.5 Definition of Baseline values

The Baseline value derived within the N01269 analysis database will be used as the Baseline for EP0132 for the following variables:

- Demographics (including body weight and height)
- QTcB (ECG)
- Clinical laboratory assessments
- Vital signs
- Neurological examination (including psychiatric and mental status)
- EpiTrack Junior
- PedsQL

In cases where CFB is assessed, the change from N01269 Baseline will be calculated.

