10.3 Clinical laboratory evaluations

10.3.1 Hematology, Clinical chemistry, Endocrinology and Urinalysis parameters

Hematology, clinical chemistry, and urinalysis variables are assessed at MEV, FEV, YEV, FV, and EDV, and will also be assessed at SV if abnormal at the FV or EDV. For study participants on study drug for more than 12 months, laboratory assessments at MEV can be omitted.

Endocrinology variables are assessed at the YEV/FV for study participants aged <18 years.

Observed results as well as CFB will be summarized descriptively, by visit, for all laboratory variables.

The definition of PCS is described in [Section 3.4](#). The criteria for a laboratory value to be PCS are defined in [Section 13.1.1](#) and [Section 13.1.2](#). All laboratory measurements will be assessed to determine if they meet PCS criteria. The number and percentage of study participants with PCST values for each laboratory variable (ie, PCST low value, PCST high value) for hematology, biochemistry, endocrinology and urinalysis will be summarized, over all visits (including unscheduled visits) and by visit separately. Percentages in the overall summary will be relative to the number of study participants with at least one assessment on or after the first dose of BRV in EP0132. Percentages in the by visit summary will be relative to the number of study participants with a measurement at the visit. Note that the urinalysis variables nitrites, pH, and specific gravity will not be assessed against PCS criteria and thus will be listed only.

For female participants of childbearing potential, a urine pregnancy test is performed at MEV, FEV, YEV, FV or EDV as applicable, and SV. A urine pregnancy test may also be performed at unscheduled visits. Serum pregnancy tests are performed for PDILI assessments and local laboratory assessments. Pregnancy test results will not be summarized.

Summaries of laboratory variables will only summarize variables planned per the protocol, however, both planned and unplanned laboratory variables will be provided in data listings. Unscheduled laboratory tests conducted by local laboratories are unplanned so will be included in the listings only.

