13.1.2 Urinalysis parameters

Urinalysis parameters assessed in this study and their possible values are specified in [Table 13-2](#).

Table 13-2: Urinalysis parameters and possible values

PARAMETER	Possible Values
Bilirubin	NEGATIVE, TRACE, 1+, 2+, 3+
Blood	NEGATIVE, TRACE, 1+, 2+, 3+
Glucose	NEGATIVE, TRACE, 1+, 2+, 3+
Ketones	NEGATIVE, TRACE, 1+, 2+, 3+, 4+
Leukocyte Esterase	NEGATIVE, TRACE, 1+, 2+, 3+
Nitrite	NEGATIVE, POSITIVE
pH	5.0, 5.5, 6.0, 6.5, 7.0, 7.5, 8.0, 8.5, >8.5
Protein	NEGATIVE, TRACE, 1+, 2+, 3+, 4+
Specific Gravity	Numeric
Urobilinogen	NORMAL, 1+, 2+, 3+

Qualitative urine parameters are generally reported by a descriptive score, which differs among laboratories. For data analysis purpose, a four-point scale is used. Five-point, six-point, or seven-point scales will be collapsed into a four-point scale first. A value is considered PCST if an upward shift of at least 2 points from the Baseline occurs under investigational treatment. To collapse the results in a five-point scale into a four-point scale, the lowest 2 positive results will be combined as per [Table 13-3](#).

Table 13-3: Conversion of results in a five-point scale into a four-point scale

Original Five-point Scale	Four-point Scale
Negative/None	Negative/None
Trace/Rare/Mild/A Few	Trace/1+/Rare/Mild/A Few
1+	
2+/Mod	2+/Mod

Table 13-3: Conversion of results in a five-point scale into a four-point scale

Original Five-point Scale	Four-point Scale
3+/Sev	3+/Sev

Mod=Moderate, Sev = Severe

The original scale and four-point scale for PCST of each urinalysis parameter is described in **Table 13-4**. Nitrates are not classified into 4-point scales, as there are only 2 values, and pH is not classified into 4-point scales as low and high pH values may be considered as good or bad.

Table 13-4: Urinalysis 4-point scales for PCS criteria

	Four-point Scale			
PARAMETER	Negative	1+	2+	3+
Bilirubin	Negative	1+	2+	3+
Blood	Negative	Trace, 1+	2+	3+
Glucose	Negative	Trace, 1+	2+	3+
Ketones	Negative	Trace, 1+	2+	3+, 4+
Leukocyte Esterase	Negative	Trace, 1+	2+	3+
Protein	Negative	Trace, 1+	2+	3+, 4+
Urobilinogen	Normal	1+	2+	3+

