13.1.3 Vital signs and body weight

Table 13-5: Vital signs and body weight PCS criteria

Parameter	Age Range	PCS Criteria
Pulse Rate (beats/minute)	6m - <3y	<90 >150
	3y - <12y	<60 >130
	12y - <17y	<50 >120
	≥17y	<50 and a decrease from Baseline of ≥15 >120 and an increase from Baseline of ≥15
Systolic Blood Pressure (mmHg)	6m - <3y	<70 >120
	3y - <12y	<80

Table 13-5: Vital signs and body weight PCS criteria

Parameter	Age Range	PCS Criteria
		>140
	12y - <17y	<90 >160
	≥17y	≤ 90 and a decrease from Baseline of ≥20 ≥ 180 and an increase from Baseline of ≥20
Diastolic Blood Pressure (mmHg)	6m - <3y	<45 >75
	3y - <12y	<50 >80
	12y - <17y	<50 >105
	≥17y	<50 and a decrease from Baseline of ≥15 >105 and an increase from Baseline of ≥ 15
Respiratory Rate (breaths/minute)	6m - <3y	<20 >45
	3y - <12y	<15 >35
	≥12y	<10 >25
Temperature	>1m	>101.0F (38.3.0C)
Body Weight ^a	1m - <17y	Outside of < 3% or > 97% percentile of the normal body weight based on gender and the age of study participant on date of weight assessment ^b
	≥17y	≥ 10% CFB (an increase or a decrease)

C = Celsius, F = Fahrenheit^b

^a Study participants who turn ≥17y during the EP0132 study, will continue to be assessed in the 1m - <17y category.

^b Assessment will be based on the growth charts from CDC https://www.cdc.gov/growthcharts/clinical_charts.htm

For the assessment of body weight PCS criteria, the participant's age at EP0132 EV will be used to determine the age category as specified in the "Age Range" column of Table 13-5 and

consequently the methodology (ie, percentage change or percentiles) to be used in the assessment of PCS measurements as specified in the “PCS Criteria” column of [Table 13-5](#).

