13.1.4 ECG

Table 13-6: QTcB interval PCS criteria

Parameter	Age	PCS criteria
QTcB interval (ms)	6m-<3y	>450, or >15% increase from Baseline
	3y-<12y	>450, or >15% increase from Baseline
	12y-<17y	>450, or >15% increase from Baseline
	≥17y	>500 or ≥60 ms increase from Baseline

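### For fixed-threshold safety criteria, the planned PCST percentages mix abnormalities already present at N01269 Baseline with new ones, and no planned summary separates them (minor)

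*SAP*

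**What the plan says.** SAP 3.4 treats as PCST all values that satisfy the criteria of Section 13.1 and "which occur any time after the first dose of BRV has been taken in EP0132". It adds that such values "will be considered PCST regardless of whether or not they met the criteria for PCS previously". Age-dependent criteria are judged by the participant's age at the visit.

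SAP 3.5 fixes the reference: "The Baseline value derived within the N01269 analysis database will be used as the Baseline for EP0132", and its list covers clinical laboratory assessments, vital signs and QTcB. Baseline status can therefore be derived for these parameters.

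The denominator for the over-all-visits summary in SAP 10.3.1 is "relative to the number of study participants with at least one assessment on or after the first dose of BRV in EP0132", and SAP 10.4.1 uses the same one. Neither removes or separates participants who met the criterion at Baseline. QTcB PCST is planned by visit only (SAP 10.4.2).

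Some criteria in Section 13.1 have a change from Baseline built in:
- Urinalysis (13.1.2): "A value is considered PCST if an upward shift of at least 2 points from the Baseline occurs under investigational treatment".
- Pulse and blood pressure from age 17 (13.1.3); for low pulse the rule is "<50 and a decrease from Baseline of ≥15".
- Body weight from age 17 (13.1.3).
- The change limbs of QTcB (13.1.4).

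The remaining criteria are fixed thresholds: hematology, chemistry and thyroxine in Table 13-1; under-17 pulse and blood pressure, respiratory rate and temperature in Table 13-5; and the absolute QTcB limits in Table 13-6. For QTcB under 17 the rule is ">450, or >15% increase from Baseline", so exceeding 450 ms is enough by itself.

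**The concern.** A reader will take a table headed treatment-emergent to describe abnormalities that appeared on treatment. For a fixed threshold, a low platelet count or long QTcB that was present at Baseline and never moved counts the same as a new one. By-visit tables can count the same stable participant at each visit.

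Adverse events are handled differently: under SAP 10.2 an event is treatment-emergent only if its onset is on or after the day of first dose.

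The study has one arm, so Baseline is the only comparison inside it. Protocol 8.1.7 foresees participants arriving from N01269 with clinically significant laboratory abnormalities, so the case is not hypothetical. What is at stake is how the PCST tables are read. No test or decision rule depends on them.

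**Working it through.** The documents give no PCST rate and no Baseline rate, so there is no stated figure to reproduce. The check has two parts.

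**1. Does any planned output separate persisting from new?**

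| Planned output | Shows Baseline status for the same criterion? |
|---|---|
| PCST counts (SAP 10.3.1, 10.4.1, 10.4.2) | No |
| Change-from-Baseline statistics by visit | No; group summaries do not show who crossed a threshold |
| ECG shift table (10.4.2) | No; it uses normal/abnormal categories, not the QTcB criterion |
| Plots of Baseline against maximum (10.3.2) | In part; AST, ALT, ALP and total bilirubin only, as multiples of the upper limit of normal |
| Listings (10.3.1, 10.4.1, 10.4.2) | Only by reconstruction, participant by participant |

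**2. How much could it matter?**

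Inputs:
- N = 140, the approximate enrollment (SAP 2.4), assuming that all have a post-dose assessment.
- p = share who met the criterion at Baseline and meet it again at least once after first dose (assumed).
- q = share of the others who newly meet it (assumed).

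Formulas: reported share = p + (1 − p) × q; new participants = N × (1 − p) × q.

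- p = 5%, q = 2%: 0.05 + 0.95 × 0.02 = 0.069. Reported: 140 × 0.069 = 9.7. New: 140 × 0.95 × 0.02 = 2.7.
- p = 2%, q = 5%: 0.02 + 0.98 × 0.05 = 0.069. Reported: again 9.7. New: 140 × 0.98 × 0.05 = 6.9.

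The same reported 6.9% thus fits about 3 new cases or about 7.

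Reported PCST share over a range of assumptions:

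| p | q = 0% | q = 2% | q = 5% |
|---|---|---|---|
| 0% | 0.00% | 2.00% | 5.00% |
| 1% | 1.00% | 2.98% | 5.95% |
| 3% | 3.00% | 4.94% | 7.85% |
| 5% | 5.00% | 6.90% | 9.75% |
| 10% | 10.00% | 11.80% | 14.50% |

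Among participants who did not meet the criterion at Baseline, the share is q in every row. With p near zero the two readings coincide.

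**The case against.** The case against is substantial, and most of it stands.

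- **The rule is disclosed, prespecified and one-sided.** It can only over-count, so it drops no abnormal value. This stands.
- **PCST is not an endpoint measure.** SAP Table 3-1 gives visit values and change from Baseline as the measures for laboratory tests, ECG parameters and vital signs. The primary endpoints are TEAEs and TEAEs leading to discontinuation, and no inferential testing is planned (SAP 4.3). This stands and limits the weight of the point.
- **Baseline information is partly available** through change summaries, the ECG shift table, liver plots and listings. This stands in part: none of them tabulates Baseline status for the PCST criterion.
- **Entry criteria limit carry-over.** Protocol 5.2 excludes clinically relevant ECG abnormality, hepatic impairment and laboratory values that could affect safe participation. This may make p small, but the documents do not say how small.

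A reader might infer two stronger things.

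The first is that the SAP contradicts itself, because urinalysis and the age-17-and-over vital signs need a change from Baseline. The text does not support that. Section 3.4 applies one timing rule to whatever criteria Section 13.1 sets, and those criteria may differ by parameter and age. The contrast shows only that the tables do not all mean the same thing.

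The second is that the term treatment-emergent should be withheld from anyone who met the criterion at Baseline. That would remove the label from a participant whose abnormal platelet count then falls much further, and from one whose Baseline is missing. The latter would run against SAP 4.1.4.4, which treats an adverse event of undeterminable status as treatment-emergent.

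**Conclusion.** The point holds as a minor one about presentation. For the fixed-threshold criteria, PCST percentages combine persisting and new abnormalities, and no planned summary separates them. Nothing elsewhere in the SAP overrides 3.4 for these criteria.

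The size is unknown. The 6.9% example rests on assumed rates and shows only that one reported percentage can describe different safety pictures. The documents do not support a claim that PCST rates will be inflated by any particular amount, or that the primary safety results are affected.

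The point does not extend to criteria that already include a change from Baseline. Under-17 body weight ("Outside of < 3% or > 97% percentile of the normal body weight") also lacks a Baseline comparison, but it has its own age rule in 13.1.3, with the category set by age at the EP0132 Entry Visit. It is left outside this point.

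**What to change.** In SAP 3.4, 10.3.1, 10.4.1 and 10.4.2:

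1. Keep the PCST count and its label as they are.
2. For the fixed-threshold criteria, split the over-all-visits PCST count by N01269 Baseline status on the criterion: not met, met, Baseline missing. For QTcB, split the by-visit count, since that is the one planned.
3. Judge the Baseline value by age at Baseline, in line with the age-at-visit rule in 3.4. Add a footnote that an unchanged value can become PCS when a child enters a new age band. For example, the upper pulse limit falls from 130 to 120 at age 12.
4. Describe only the 'not met' row as newly PCS relative to Baseline. Keep the 'met' and 'missing' rows visible, so that worsening in already-abnormal participants is not lost.
5. Use N01269 Baseline, not the Entry Visit, so that abnormalities which arose during the core study still count as new.
6. Exempt criteria that already include a change: urinalysis; pulse, blood pressure and body weight from age 17; and QTcB values that qualify only through a change limb.

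The Baseline values are already needed for the change-from-Baseline summaries, so no new data are required. The cost is a few lines of SAP text and slightly longer tables.

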3.5 Definition of Baseline values

The Baseline value derived within the N01269 analysis database will be used as the Baseline for EP0132 for the following variables:

- Demographics (including body weight and height)
- QTcB (ECG)
- Clinical laboratory assessments
- Vital signs
- Neurological examination (including psychiatric and mental status)
- EpiTrack Junior
- PedsQL

In cases where CFB is assessed, the change from N01269 Baseline will be calculated.

3.6 Protocol deviations

Important protocol deviations (IPDs) are deviations from the protocol that could potentially impact the interpretation of the study data. The criteria for identifying IPDs and the classification of IPDs will be defined separately in the Specifications for IPDs document. To the extent feasible, rules for identifying IPDs will be defined without review of the data and without consideration of the frequency of occurrence of such deviations. Whenever possible, criteria for identifying IPDs will be implemented algorithmically to ensure consistency in the classification of IPDs across all study participants.

All completed COVID-19 impact eCRF pages will be discussed in IPD meetings in order to determine if any such events are to be considered and reported as IPDs.

All other IPDs will also be reviewed and discussed in IPD meetings.

3.7 Analysis sets

3.7.1 All Study Participants Screened Set

The All Study Participants Screened (ASPS) Set will consist of all screened study participants who gave informed consent (and informed assent where required).

3.7.2 Safety Set

The Safety Set (SS) will consist of all enrolled study participants who took at least 1 dose of study drug in the LTFU study. All analyses will be performed on the SS, except where specifically noted.

3.7.3 PK Analysis Set

The PK Analysis Set (PKAS) will consist of all enrolled study participants who during the study took at least 1 dose of study drug in the LTFU study and had at least 1 PK measurement. This measurement may be quantifiable or below limit of quantification (BLQ).

Participants will be included in the PKAS only if the date and time of both dosing and PK sampling is available for at least 1 PK measurement.

3.8 Treatment assignment and treatment groups

This is an open-label study. Due to the large variation in the doses a study participant may receive throughout the study, outputs will be produced by actual syndrome (CAE/JAE) and all participants only. Selected outputs may also be produced by modal dose or maximum BRV dose.

3.9 Multicenter studies

Study outcomes will not be assessed for individual investigator sites and individual countries due to the low expected enrollment within each investigator site.

3.10 Center pooling strategy

The number of study participants for most sites is expected to be low. No site pooling strategy is defined for this study.

3.11 Coding dictionaries

Medical history and AEs will be coded using the Medical Dictionary for Regulatory Activities (MedDRA) version 18.1. Medications will be coded using the World Health Organization Drug Reference List version SEP 2020. Medical procedures will not be coded.

3.12 Changes to protocol-defined analyses

3.12.1 Concomitant use of AEDs and the impact on secondary objectives

The secondary objectives in the protocol specify the analysis of absence seizure freedom data (based on EEG and diary data) and how to handle the concomitant use of AEDs in the analysis. Specifically, the protocol has the following text:

For ‘Absence seizure freedom within 4 days prior to or during the 1-hour EEG at each applicable visit’:

‘The intercurrent event of concomitant use of any permitted AED, including benzodiazepines, within 4 days prior to or during the 1-hour EEG is handled in the definition of the participant-level variable implementing a composite strategy in which receiving any permitted concomitant AED, including benzodiazepines, within 4 days prior to or during the 1-hour EEG is counted as nonresponse (ie, considered as having absence seizures during the EEG).’

For ‘Absence seizure freedom based on diary over the entire evaluation period and by 3-month time intervals’:

‘The intercurrent event of concomitant use of any permitted AED, including benzodiazepines, during each applicable 3-month period is handled in the definition of the participant-level variable implementing a composite strategy in which receiving any permitted concomitant AED, including benzodiazepines, in the 3-month period or during the visit is counted as nonresponse (ie, considered as having absence seizures).’

The SAP has been updated to remove the word ‘permitted’ as all AEDs (both permitted and prohibited) may have an impact on the efficacy outcomes and should be considered in the analysis.

3.12.2 Truncation of absence seizure freedom data to Month 24 and the impact on secondary objectives

Per the protocol the secondary objectives and endpoints for absence seizure freedom and consecutive absence seizure freedom based on EEG and diary data do not specify the timeframe over which absence seizure freedom is assessed. Specifically, the protocol has the following text for these endpoints:

- ‘Absence seizure freedom within 4 days prior to or during the 1-hour EEG at each applicable visit’
- ‘Absence seizure freedom based on diary over the entire evaluation period and by 3-month time intervals’
- ‘Consecutive absence seizure freedom in 6-month periods based on EEG’
- ‘Consecutive absence seizure freedom in 6-month periods based on diary’

The SAP has been updated to include a timeframe for these endpoints. The absence seizure freedom and consecutive absence seizure freedom based on 1-hour EEG endpoint will be analyzed up to Month 24 YEV. The absence seizure freedom and consecutive absence seizure freedom based on seizure diary will be analyzed over the Evaluation Period truncated at the Month 24 YEV; the 3-month and 6-month time intervals will be analyzed up to Months 22-24 and Months 19-24, respectively.

